### 10.3. Secondary Endpoints

The following secondary efficacy endpoints will be explored:

- S1. Comparison of global haemostatic response to *Octaplex* versus FP, defined as 'positive' if no additional haemostatic intervention (as per the primary endpoint) is required and haemoglobin levels decrease by <30% (after accounting for red cell transfusions) from 60 minutes to 24 hours after initiation of the first dose of IMP. The 24-hour haemoglobin result will be reduced by 1 g/dL for each unit of RBC transfused from 60 minutes to 24 hours.
- S2. Comparison of the total amount of chest tube drainage at 12 and 24 hours after chest closure between the *Octaplex* and FP groups.
- S3. Comparison of the incidence of severe to massive bleeding, using a modification of the universal definition of perioperative bleeding (UDPB) in cardiac surgery and its individual components during the first 24 hours after start of surgery, after the end of CPB and after IMP initiation, between the *Octaplex* and FP groups.
- S4. Comparison of the mean number of total allogeneic blood components – including red cells, platelets and all (IMP and non-IMP) FP – administered during the first 24 hours after the end of CPB, between the *Octaplex* and FP groups.
- S5. Comparison of the mean number of total non-IMP allogeneic blood components – including red cells, platelets and non-IMP FP – administered during the first 24 hours after the end of CPB, between the *Octaplex* and FP groups.
- S6. Comparison of the mean number of total non-IMP allogeneic blood components – including red cells, platelets, cryoprecipitate and non-IMP FP – administered during the first 24 hours and 7 days after IMP initiation, between the *Octaplex* and FP groups.
- S7. Comparison of the mean number of individual allogeneic blood components – including red cells, platelets, cryoprecipitate and non-IMP FP – administered during the first 24 hours and 7 days after the start of surgery, after the end of CPB and after IMP initiation, between the *Octaplex* and FP groups.
- S8. Comparison of the incidence of transfusion of individual allogeneic blood components – including red cells, platelets, cryoprecipitate and non-IMP FP – during the first 24 hours and 7 days after the start of surgery, after the end of CPB and after IMP initiation, between the *Octaplex* and FP groups.

- S9. Comparison of the incidence of administration of non-IMP coagulation factor products – including fibrinogen concentrate and activated recombinant factor VII – during the first 24 hours and 7 days after the start of surgery, after the end of CPB and after IMP initiation, between the *Octaplex* and FP groups.
- S10. Comparison of the incidence of intracerebral haemorrhage during the first 24 hours after start of surgery, after the end of CPB and after IMP initiation between the *Octaplex* and FP groups.
- S11. Comparison of the incidence of gastrointestinal haemorrhage during the first 24 hours after start of surgery, after the end of CPB and after IMP initiation between the *Octaplex* and FP groups.
- S12. Comparison of the incidence of surgical re-exploration for bleeding during the first 24 hours after start of surgery, after the end of CPB and after IMP initiation between the *Octaplex* and FP groups.
- S13. Comparison of the change in INR, from within 30 minutes before to within 60 minutes after the initiation of IMP administration, between the *Octaplex* and FP groups; INR reduction will be considered successful if the magnitude of the reduction is >1.0 or the post-treatment level drops below 1.5.
- S14. Comparison of the changes in other coagulation parameters, including PT, aPTT, fibrinogen activity, ROTEM EXTEM CT and MCF and platelets, from within 75 minutes before to within 75 minutes after the initiation of IMP administration, between the *Octaplex* and FP groups. For a given parameter, if there are multiple results in the window within 75 minutes before to initiation of IMP administration, the most recent result before IMP initiation will be used. If there are multiple results in the window within 75 minutes after the initiation of IMP administration, the earliest result after IMP administration will be used.
- S15. Comparison of time elapsed from initiation of the first dose of IMP to arrival at the ICU room between the *Octaplex* and FP groups. Patients in the ICU at the time of first dose of IMP will be excluded from this analysis.

The following analysis methods will be applied to the different endpoints, according to their data type:

The analysis of categorical variables (S1, S3, S8, S9, S10, S11, S12) will present relative frequency tables and estimates of the proportions with 95% confidence intervals separately in the treatment groups. The proportions will be compared between the treatment groups in the context of a logistic regression model.

The analysis of continuous variables (S2, S13, S14, S15) will present descriptive statistics of the sampling distribution and the differences between treatment groups. Also, 95% confidence intervals and results of F-test of the treatment group differences will be reported in the context of an ANOVA model.

The analysis of integer count variables (S4, S5, S6, S7) will present descriptive statistics of the sampling distribution and the differences between treatment groups. Treatment group comparisons for variables (S4, S5, S6, S7) will be performed in the context of a counting regression model for the ABCs and their components (SAS PROC GENMOD with Negative-Binomial distribution). Tests and 95% confidence intervals for the treatment group differences will be derived from this statistical model and reported.

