Randomisation		X			
IMP (PCC or FP) administration ⁴			X		
Baseline data					
Demographics			X		
Medical history			X		
Preoperative medications			X		
Laboratory assessments			X		
Surgical data					
Bleeding Score			X ²		
Intraoperative medications			X		
CPB time			X		
Cross-clamp time			X		
Circulatory arrest			X		
Fluid intake and output monitoring			X		
Inotropes and vasopressors			X		
Start and end time of IMP administration			X		
OR length of stay			X		
Laboratory assessments					
Clinical chemistry ⁵			X	X	
Haematology (CBC) ⁵			X ⁶	X ⁷	
Coagulation measures ^{5,8}			X ⁹	X	
Safety laboratory analyses ⁵			X	X	
INR			X ¹⁰		
Transfusions and haemostatic therapies and timings					
Second dose of PCC (IMP), if needed ¹¹			X		
Second dose of FP (IMP), if needed ¹¹			X		
FP (non-IMP)			X	X	
RBCs			X	X	
Pooled and apheresis platelets			X	X	
Cryoprecipitate			X	X	
Fibrinogen concentrate			X	X	
Activated recombinant factor VII			X	X	
Other haemostatic products			X	X	
Blood loss determination					

Total chest tube drainage at 1, 6 12 hours and 24 hours after chest closure			X	X	
Bleeding-related clinical endpoints					
Occurrence of intracerebral haemorrhage ¹²			X	X	
Occurrence of gastrointestinal haemorrhage ¹²			X	X	
Occurrence of surgical re-exploration ¹²			X	X	
Extubation time			X	(X)	(X)
ICU length of stay				(X)	(X)
Hospital length of stay				(X)	(X)
Hospital readmissions					X
AEs and SAEs			X	X	X
Concomitant medications			X	X	X
Patient survival					X

AE, adverse event; aPTT, activated partial thromboplastin time; CBC, complete blood count; CPB, cardiopulmonary bypass; CT, clotting time; DC, discharge; FP, frozen plasma; ICU, intensive care unit; IMP, investigational medicinal product; INR, international normalised ratio (INR); MCF, maximum clot firmness; OR, operating room; PCC, prothrombin complex concentrate; POD, postoperative day; PT, prothrombin time; RBC, red blood cell; SAE, serious adverse event;

¹ For any specified activity that cannot be completed during the first visit after IMP initiation, additional visits will be made on postoperative day 1 until all study data are obtained

² Inclusion criteria 1 and 4, and all exclusion criteria checked for eligibility at the screening visit. If screening is performed before the day of surgery, exclusion criterion 3 (i.e., severe right heart failure [clinical diagnosis ± echocardiography]) will be rechecked on the day of surgery

³ After the start of surgery

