Overall, the PCC group received a median (IQR) of 24.9 (21.8–27.0) IU/kg of PCC [two patients (3.7%; 95% CI 0.4–12.7%) required FP after PCC], and the FP group received a median (IQR) of 12.5 (10.0–15.0) mL/kg of FP [four patients (8.5%; 95% CI 2.4–20.4%) required >2 doses of FP]. Median (IQR) 12-hour chest tube drainage was 310 (250–455) mL and 500 (310–750) mL in the PCC and FP groups, respectively ($P<0.001$). One of the primary measures of haemostatic effects was treatment response, based on receipt of any haemostatic therapies from 60 minutes to 4 and 24 hours after initiation of study treatment. Haemostatic therapy was not required at the 4-hour time point for 43 patients (79.6%) in the PCC group and 32 patients (68.1%) in the FP group ($P=0.25$), nor at the 24-hour time point for 41 patients (75.9%) in the PCC group and 31 patients (66.0%) in the FP group ($P=0.28$). Another primary outcome measure was cumulative and individual allogeneic blood component units administered within 24 hours after the start of surgery. Median (IQR) 24-hour post-bypass cumulative allogeneic transfusions, including red cells, platelets and all (IMP + non-IMP) FP were 5.0 (4.0–9.0) units in the PCC group and 12.0 (7.0–19.0) in the FP group; ratio 0.56, 95% CI 0.43–0.73; $P<0.001$. Excluding IMP FP, the median (IQR) cumulative allogeneic transfusions were 5.0 (4.0–9.0) and 8.0 (4.0–15.0) units, respectively; ratio 0.78, 95% CI 0.58–1.06; $P=0.11$. For red cells alone, the median (IQR) was 1.0 (0.0–2.0) and 2.0 (1.0–3.0) units, respectively; ratio 0.53, 95% CI 0.36–0.78; $P<0.001$. Adverse event profiles were similar.

This pilot study showed that 4-factor PCC may be a suitable substitute for FP for mitigation of bleeding in cardiac surgery and validated the study methodology and dosing that will be used for the proposed trial. It also clearly illustrated that a large, multicentre, confirmatory trial is warranted to determine the relative risk-benefit profiles of these two therapeutics.

Purpose of the Study

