- Measure haemoglobin within 30 ± 15 minutes before and at 60 ± 15 minutes after IMP initiation
- Measure INR within 30 ± 15 minutes before and at 60 ± 15 minutes after IMP initiation and document results
- Administer second dose of IMP, if needed
- Collect all transfusions and haemostatic therapies
- Collect chest tube drainage at 1, 6, 12 and 24 hours after chest closure
- Measure haemoglobin at 24 hours ± 1 hour after IMP initiation and document results
- Collect extubation time
- Collect concomitant medications
- Collect AEs and SAEs

6.1.4 Visit 3 (POD 2-7): Days 2-7 after IMP initiation (or at discharge, if earlier)

- Collect daily laboratory assessments where available as part of routine care
 - Chemistry (sodium, potassium, chloride, bicarbonate, pH)

- Haematology (complete blood count)
- Coagulation profile (e.g. PT, aPTT, INR, plasma fibrinogen level, ROTEM EXTEM CT and MCF, ROTEM FIBTEM MCF platelet count, platelet function)
- Safety labs (creatinine, liver function tests [ALT, ALP], bilirubin, troponin)
- Collect all transfusions and haemostatic therapies
- Record incidence of intracerebral haemorrhage, gastrointestinal haemorrhage and surgical re-exploration.
- Collect extubation time (if applicable)
- Collect length of stay in the ICU and hospital (if applicable)
- Collect concomitant medications
- Collect AEs and SAEs

6.1.5 Visit 4 (POD 30): Day 30 after IMP initiation (in person if in hospital, or by phone)

- Collect concomitant medications
- Collect AEs and SAEs
- Collect extubation time (if applicable)
- Collect length of stay in the ICU (if applicable)
- Collect length of stay in the hospital (if hospital stay is extended) and hospital readmissions
- Document patient outcome and survival at 30 days (still in hospital; dead or alive)

After Visit 4 or on POD-30, the clinical study is considered completed for the patient. No further study-related assessments will be performed, unless safety concerns (e.g., ongoing AEs) require follow-up.

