7.2.2 Assessments for Secondary Efficacy Endpoints

7.2.2.1 Global Haemostatic Response

A secondary endpoint of global haemostatic response is included to provide supportive evidence of haemostatic effectiveness. This will be based on the haemostatic efficacy scale developed by Sarode and colleagues [69] (in discussion with the Food and Drug Administration), modified to reflect the special considerations of haemorrhage during cardiac surgery. Global haemostatic response will be considered as 'positive' if no additional haemostatic intervention (as per **Table 4**) is required *and* haemoglobin levels decrease by <30% (after accounting for red cell transfusions) in the time window from 60 minutes to 24 hours after initiation of the first IMP dose. Global haemostatic response will be considered as 'negative' if additional haemostatic intervention is required *or* haemoglobin levels decrease by ≥30% (after accounting for red cell transfusions) from 60 minutes to 24 hours after initiation of the first IMP dose.

Table 4: Objective Criteria for Determination of Global Haemostatic Response, Adapted from Sarode et al. 2013

Global Haemostatic Response	Haemostatic Intervention	Drop in Haemoglobin
Excellent (positive)	No additional coagulation interventions ¹ administered between 1 and 24 hours after initiation of infusion ²	<15% decrease in haemoglobin between 1 and 24 hours after initiation of infusion ^{2,3}
Good (positive)	No additional coagulation interventions ¹ administered between 1 and 24 hours after initiation of infusion ²	15% to <30% decrease in haemoglobin between 1 and 24 hours after initiation of infusion ^{2,3}
Poor (negative)	Additional coagulation interventions ¹ administered between 1 and 24 hours after initiation of infusion ²	≥30% decrease in haemoglobin between 1 and 24 hours after initiation of infusion ^{2,3}

¹ Administration of any systemic haemostatic agents (including platelets, cryoprecipitate, fibrinogen concentrate, activated recombinant factor VII, other coagulation factor products or a second dose of IMP) or any haemostatic interventions (including surgical re-opening for bleeding).

² The 60-minute period allows for the administration of the IMP and establishment of treatment effect.

³ Each unit of RBC transfused during this time period will be counted as a drop of 1.0 g/dL in haemoglobin.

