7.3.6.2 Local Laboratory

Table 6 summarises all test parameters performed as part of standard of care, the results of which will be collected as available.

Table 6 Test Parameters and Laboratories

Test	Material needed	Responsible Laboratory
Coagulation profile		
Point-of-care INR	Fresh blood	Local
(PT, aPTT, INR, fibrinogen activity via Clauss assay)	Citrated blood	Local
*ROTEM EXTEM CT	Citrated blood	Local
*ROTEM EXTEM MCF	Citrated blood	Local
*ROTEM FIBTEM MCF	Citrated blood	Local
PlateletWorks		
Haematology – standard panel as per local lab	Citrated blood	Local
Clinical chemistry – standard panel as per local lab	Serum	Local
Safety laboratory analyses		
Troponin	Serum	Local
ALT/ALP	Serum	Local
Bilirubin	Serum	Local
Creatinine	Serum	Local

ALT, alanine aminotransferase; ALP, alkaline phosphatase; CT, clotting time; MCF, maximum clot firmness; PT, prothrombin time; aPTT, activated partial thromboplastin time; ROTEM, thromboelastometry

*ROTEM or TEG can be measured

The haemoglobin and INR measurements will be performed at preestablished time points (**Table 7**).

Table 7 Mandatory Test Parameters and Laboratories

Test	Material needed	Responsible laboratory
Coagulation profile		
Point-of-care INR	Fresh blood Citrated blood	Local Local
Haematology		
Haemoglobin	Citrated blood	Local

Blood Sampling

All blood sampling will be performed as per standard practice at the local institution.

The *actual* time of blood sampling will be recorded. If the draw time is not recorded for samples processed in the laboratory, the draw time will be estimated based on the received time in the laboratory minus 10 minutes. For ROTEM and PlateletWorks, if the exact draw time is not recorded, the time for start of testing will be used for draw time.

Citrated and Fresh Blood

Citrated and fresh blood as required by the local laboratory will be collected and processed in accordance with local requirements.

Serum

Serum will be obtained for the determination of clinical chemistry, haematology, and safety labs (ALT, ALP, creatinine, bilirubin, troponin), where a serum blood sample has been collected.

Recording of Clinically Significant Abnormal Laboratory Values as AEs/ADRs

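### The S1 haemoglobin correction counts red-cell units on the nominal 60-minute-to-24-hour clock rather than between the two actual blood draws, so a unit given near either edge can be wrongly subtracted or wrongly omitted

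*SAP*

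**What the plan says.** S1 is positive when two conditions hold. No haemostatic intervention is needed, and the haemoglobin criterion is met, which reads: "haemoglobin levels decrease by <30% (after accounting for red cell transfusions) from 60 minutes to 24 hours after initiation of the first dose of IMP". SAP 10.3 then gives the red-cell rule: "The 24-hour haemoglobin result will be reduced by 1 g/dL for each unit of RBC transfused from 60 minutes to 24 hours". The protocol's counterpart is footnote 3 to Table 4 (7.2.2.1): "Each unit of RBC transfused during this time period will be counted as a drop of 1.0 g/dL in haemoglobin". The period meant there is the table's own column, 1 to 24 hours after the start of infusion.

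The sampling tolerances are in Protocol 6.1.3 (Visit 2) and are repeated in Table 2 (6.1.6). For the reference value: "Measure haemoglobin within 30 ± 15 minutes before and at 60 ± 15 minutes after IMP initiation". For the later value: "Measure haemoglobin at 24 hours ± 1 hour after IMP initiation and document results".

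The data for a finer rule are already collected. Protocol 7.3.6.2 provides that the actual "time of blood sampling will be recorded", with a fallback estimate if a laboratory draw time is missing. The flow chart (Table 1) has a block headed "Transfusions and haemostatic therapies and timings".

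SAP Appendix 1 repeats the definition of global response but gives no rule for matching units to samples. SAP 10.3 does set sample-selection rules for S14. It sets none for S1.

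**The concern.** A red-cell correction should remove the effect of units given between the two samples being compared. The written rule uses fixed clock times, and the samples need not fall on them. Four situations arise with draws that are fully compliant:

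- **Late 60-minute draw:** a unit given after 60 minutes but before the draw is already in the reference value, yet it is subtracted again.
- **Early 60-minute draw:** a unit given after the draw but before 60 minutes raises the later value, yet it is not subtracted.
- **Early 24-hour draw:** a unit given after the draw but before 24 hours is not in the sample, yet it is subtracted.
- **Late 24-hour draw:** a unit given after 24 hours but before the draw is in the sample, yet it is not subtracted.

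At stake is the class of individual patients on S1, which Protocol 3.3.3 lists among several supportive endpoints and which SAP 10.3 compares between arms by logistic regression.

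**Working it through.** **Stated figure, used here only for scale.** The documents give no number for S1. The evaluable sample size of 410 (Protocol 9.1) reproduces. Inputs are 70% versus 65%, margin 0.10, one-sided 0.025 and power 90%. The Farrington-Manning null rates are 0.619 and 0.719. Then n per arm = [(1.960 × √(0.619×0.381 + 0.719×0.281) + 1.282 × √(0.70×0.30 + 0.65×0.35)) / 0.15]² = 204.4, rounded up to 205, which gives 410.

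**Width of the mismatch.** With in-tolerance draws the two clocks can differ by up to 15 minutes at the start and 60 minutes at the end. That is 75 of 1,380 minutes, or 5.4% of the window.

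**Effect of one unit.** With u units counted, decrease (%) = 100 × [H60 − (H24 − u)] / H60. One miscounted unit therefore shifts the result by 100/H60 points: 14.3 at 7 g/dL, 11.1 at 9 and 8.3 at 12.

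**Worked cases.** Assumed values: H60 = 9.0 and measured H24 = 7.2 g/dL. With u = 0 the decrease is 1.8/9.0 = 20.0%. With u = 1 it is 2.8/9.0 = 31.1%.

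| Off-time draw | Unit given at | Nominal clock | Between draws |
|---|---|---|---|
| 60-min sample at 75 min | 65 min | 31.1%, negative | 20.0%, positive |
| 60-min sample at 45 min | 50 min | 20.0%, positive | 31.1%, negative |
| 24-h sample at 23 h | 23.5 h | 31.1%, negative | 20.0%, positive |
| 24-h sample at 25 h | 24.5 h | 20.0%, positive | 31.1%, negative |

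At 9 g/dL, one over-counted unit turns a correct decrease of 18.9% to just under 30% negative. One missed unit turns a decrease of 30% to just under 41.1% positive.

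**Frequency, by simulation on assumptions that are not in the documents.**

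- Draws are uniform within tolerance.
- Red-cell units are Poisson with mean 1, 2 or 3 from 45 minutes onward.
- A share of 0%, 50% or 80% of units is front-loaded (exponential, mean 2 hours). The rest are uniform to 25 hours.
- H60 has mean 9 and SD 1.2 g/dL.
- The corrected fall has mean 0.5 and SD 1.2 g/dL, plus 0.5 g/dL per unit.

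| Mean units | Patients with a miscounted unit (0 / 50 / 80% front-loaded) | Haemoglobin component changes side of 30% |
|---|---|---|
| 1 | 2.5 / 3.9 / 4.7% | 0.4 / 0.6 / 0.8% |
| 2 | 5.0 / 7.6 / 9.3% | 1.1 / 1.7 / 2.1% |
| 3 | 7.3 / 11.3 / 13.5% | 1.8 / 2.8 / 3.4% |

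The changes split almost evenly. In the lowest scenario 0.23% of patients move to negative and 0.18% to positive; in the highest, 1.75% and 1.68%.

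An additional haemostatic intervention already makes S1 negative, so only patients without one can change class. Taking that share as 65% to 70%, from the planning rates, and treating it as independent of the change gives 410 × 0.65 × 0.0041 ≈ 1 to 410 × 0.70 × 0.0343 ≈ 10 patients.

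**The case against.** **The clock may be shorthand.** In the SAP sentence, the 24-hour result is itself a nominal label for a sample allowed at ±1 hour. The window could be read the same way, as running from the first sample to the second. That reading is possible, but the sentence does not say it, and a programmer following it literally would code fixed times. If it is what was meant, the fix only writes the intention down.

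**The correction is approximate anyway.** One g/dL per unit is a convention, and a common window is simple. This is fair, but an approximate effect size is a different matter from subtracting a unit that is not in the sample.

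**It is rare and S1 is exploratory.** This stands. A class change needs an off-time draw, a unit in that gap, a fall within about one unit of 30%, and no haemostatic intervention. S1 has no place in the confirmatory hierarchy of SAP 10.2.

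A reader might also infer more than the documents support:

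- **Bias between arms.** The pilot (Protocol 1.1) reports: "For red cells alone, the median (IQR) was 1.0 (0.0–2.0) and 2.0 (1.0–3.0) units, respectively". These are 24-hour totals measured from surgery or bypass, so they can include units given before the study product. They show nothing about use at the window edges.
- **A larger share of patients reclassified.** Draws uniform over ±15 minutes deviate by 7.5 minutes (0.125 h) on average. At an assumed 0.25 to 0.5 units per hour, that is 0.03 to 0.06 units per patient misplaced at the 60-minute edge. These are misplaced units, not changed classes.
- **An effect at the 15% cut-off.** Table 4 separates excellent from good there, but both are positive and the SAP analyses S1 as binary at 30%.

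**Conclusion.** The point holds as a defect in the S1 derivation rule: with compliant sampling, the literal rule can give the wrong haemoglobin change and, near 30%, the wrong class. The mechanism and the size per unit (about 11 points at an assumed 9 g/dL) follow from the text and arithmetic.

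The frequency does not. Roughly 1 to 10 of 410 patients, in both directions, rests wholly on the simulation's assumptions and is probably low. Two simplifications pull in opposite directions. Transfused patients may be likelier to have had an intervention, which would lower the figure. The transfusion algorithm (Protocol Figure 2) triggers red cells on haemoglobin, so a low study sample may itself prompt a unit just after the draw, which would raise it.

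A reader might infer that the S1 comparison is unreliable or tilted towards one arm. The documents do not show either. The primary endpoint and the sample size are unaffected. The rule should be corrected because the error is avoidable with data already collected.

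**What to change.** In SAP 10.3 S1, SAP Appendix 1 and footnote 3 of Protocol Table 4, count the red-cell units transfused between the draw time of the 60-minute haemoglobin sample and that of the 24-hour sample. Use the recorded draw time or, where Protocol 7.3.6.2 applies, the estimated one (laboratory receipt minus 10 minutes). State a convention for a unit that is running when a sample is drawn. Leave the haemostatic-intervention component on its 60-minute-to-24-hour clock. Report S1 with the nominal-window count as a sensitivity analysis.

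The cost is a few sentences and slightly more programming, with no new data, visits or procedures. The red-cell window would vary a little between patients, from 21.75 hours (75 minutes to 23 hours) to 24.25 hours (45 minutes to 25 hours), and would differ slightly from the intervention window. Estimated draw times remain approximate.

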6 STUDY CONDUCT

All patients ≥ 18 years old undergoing cardiac surgery with CPB at the study centres will be the potential patients in the study. Voluntarily given, written, informed consent will be obtained from the patient. Once consent has been obtained and the patients enrolled into the study, eligibility according to inclusion criteria 1 and 4 (i.e., patients ≥ 18 years old, undergoing any index cardiac surgery employing CPB, who have provided informed consent) and the exclusion criteria will be determined. If screening is performed before the day of surgery, exclusion criterion 3 (i.e., severe right heart failure [clinical diagnosis \pm echocardiography]) will be rechecked on the day of surgery.

Only patients who require coagulation factor replacement therapy during surgery will be randomised, receive study drug, and undergo the proceeding visits and assessments.

When the first order for PCC or FP is received by the blood bank/pharmacy while the patient is in the operating room, the blood bank/pharmacy technologist will confirm patient eligibility with the clinical team. Following confirmation of eligibility, the technologist will randomise the patient to PCC or FP according to the randomisation and dosing schedule and prepare and release the IMP in a tamper sealed container (with weight device in PCC containing boxes to ensure adequate concealment). Operating room personnel will remain blinded until the decision to administer the IMP is made.

IMP can be administered if bleeding is severe enough to necessitate IMP (meaning at least a grade 2 level [moderate] bleeding according to the validated Bleeding Severity Scale [78] – see Appendix 1), heparin is adequately reversed (confirmed by the return of post-protamine ACT to within 10% of pre-pump ACT) and INR is ≥ 1.5 (using the Hemochron Signature Elite; Instrumentation Laboratory). IMP can also be administered if bleeding is severe enough to require urgent therapy, in which case treatment can be initiated irrespective of the INR value. Once the decision is made to administer the IMP, the administering clinician will break the seal on the container, carry out routine safety checks, and initiate IMP administration according to the weight-based dosing recommendations: For *Octaplex*: 1500 IU if ≤ 60 kg; 2000 IU if >60 kg. For FP: 3 U if ≤ 60 kg; 4 U if >60 kg.

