#### 4.1. Inclusion/Exclusion

##### 4.1.1. Inclusion Criteria

Patients meeting the following criteria will be eligible for inclusion in the study:

1. Adult (≥18 years old) patients undergoing any index cardiac surgery employing CPB
2. Coagulation factor replacement with PCC or FP ordered in the operating room for:
  - a. Management of bleeding, or
  - b. Anticipated bleeding in a patient who has been on-pump for >2 hours or has undergone a complex procedure (e.g., aortocoronary bypass [ACB] plus aortic valve replacement)
3. Coagulation factor deficiency, either known to exist (e.g., as indicated by elevated EXTEM clotting time [CT] or INR) or suspected based on the clinical situation
4. Patients who have given written informed consent

 US sites only; in Canada informed consent will be obtained in accordance with Article 3.7A of the 2018 Tri-Council Policy Statement on the Ethical Conduct for Research Involving Humans.

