### **6.3. Full Analysis Set (FAS) Population**

The full analysis set (FAS) will be defined according to the intention-to-treat (ITT) principle and will consist of all randomised patients who provide consent and receive any amount of the intervention.

The FAS will serve as the primary analysis set. For patients who withdraw consent, data will be used up until the time consent is withdrawn.

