### **7. Statistical Methods**

All statistical analyses will be performed using the SAS® software (Version 9.4 or later).

The analysis of safety will be based on the FAS population.

The primary evaluation of overall efficacy will be performed on the FAS population. In addition, selected efficacy analyses will also be presented for the PPS population.

If not stated otherwise, the following standard descriptive statistics will be presented:

- Descriptive statistics for continuous data

Number (N), mean, standard deviation (SD), min, lower quartile, median, upper quartile and max will be presented. These descriptive statistics will be determined for measured values and optionally for differences to baseline.

- Descriptive statistics for categorical data

Absolute frequencies and percentages will be presented. Percentage bases (denominators) will be identified in the table title or footnote (i.e., all patients at risk, all non-missing cases, all cases). For changes from baseline, shift tables may be generated.

- Exploratory statistics

Although statistical methods are primarily descriptive, two-sided 95% confidence intervals may be presented for selected parameters (e.g., incidences of adverse events) in an exploratory manner.

- Listings

All recorded data will be listed by patient. Identification variable will be the patient ID.

Derived data will be stored in special analysis data sets and will be calculated as outlined in **Appendix 1**.

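### The S13 rule for INR success has no baseline condition, so it does not measure INR reduction in patients already below 1.5, and the SAP names no analysis for it

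*SAP*

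**What the plan says.** S13 (SAP 10.3, same rule in SAP 5.2 and Protocol 3.1.2) compares the change in INR around the start of IMP and adds a yes/no rule: "INR reduction will be considered successful if the magnitude of the reduction is >1.0 or the post-treatment level drops below 1.5". Neither document ties the rule to the starting INR.

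The standard route to treatment in Protocol 6 requires an INR of at least 1.5. A second route covers bleeding that needs urgent therapy, "in which case treatment can be initiated irrespective of the INR value". Eligibility does not require a raised INR either: a factor deficiency may be "suspected based on the clinical situation" (SAP 4.1.1).

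The full analysis set (SAP 6.3) "will consist of all randomised patients who provide consent and receive any amount of the intervention", and SAP 7 says: "The primary evaluation of overall efficacy will be performed on the FAS population". There is no INR condition at either place.

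On method, SAP 10.3 says: "The analysis of continuous variables (S2, S13, S14, S15) will present descriptive statistics of the sampling distribution", followed by an ANOVA. S13 does not appear among the categorical endpoints, which are compared by logistic regression. SAP Appendix 1 derives treatment response and global response but not INR success. SAP 10.3 gives handling rules for S14 (multiple results) and S15 (an exclusion), but none for S13.

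**The concern.** A success rule for INR reduction should separate patients whose INR came down from those whose INR did not. For a patient who starts below 1.5 this rule cannot do that, and its verb, *drops*, leaves the coding open. Two programmers could code the same patient in opposite ways and both claim to follow the SAP.

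Protocol 3.3.3 lists INR reduction among the endpoints meant to support the haemostatic efficacy claim, so the success proportion is likely to be quoted. As written, its denominator, its coding for low-INR patients and its between-group method would all be settled after the data are in. What is at stake is the meaning of one supportive proportion, and the size of any treatment difference later calculated from it.

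**Working it through.** **The plan's own figure.** The documents give no success rate, power or sample size for S13. The only design figure is the 410 evaluable patients for the primary endpoint, used here just to set the scale. Inputs (SAP 4.2): 70% against 65%, margin 0.10, one-sided 0.025, power 90%, Farrington-Manning test. The restricted null rates are 0.619 (PCC) and 0.719 (FP), so the null SD term is √(0.619×0.381 + 0.719×0.281) = 0.662. The alternative SD term is √(0.70×0.30 + 0.65×0.35) = 0.661. Then n = (1.960×0.662 + 1.282×0.661)² / 0.15² ≈ 204.4 per arm, rounded up to 205, or 410 in all. The figure reproduces.

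**The rule at a starting INR below 1.5.**
1. Reduction above 1.0: post-treatment INR must be below 1.5 - 1.0 = 0.5. In practice this is out of reach.
2. Post-treatment level, read as *is below 1.5*: the patient succeeds with no reduction at all, unless INR rises to 1.5 or more.
3. Post-treatment level, read as *crosses 1.5 from above*: success is impossible.

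**Effect on a success comparison, if one is made.** Let f be the share starting below 1.5 (equal in both arms), d the true difference among those starting at 1.5 or more, and g the success rate among those below 1.5. The observed difference is

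(1 - f)·d + f·(g_PCC - g_FP).

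Under reading 3, g is 0 in both arms and the result is exactly (1 - f)·d. Under reading 2 it is (1 - f)·d only if g is the same in both arms, hence *about*.

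The documents give neither f nor any INR success rate. Assume 60% (PCC) against 45% (FP) among patients starting at 1.5 or more, so d = 15 points, with 205 per arm and a two-sided 0.05 test. The two values in a cell are for all low-INR patients coded as successes / as failures. The restricted analysis uses 205×(1 - f) per arm.

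| f | Difference (points) | Odds ratio | Power, all patients | Power, restricted |
|---|---|---|---|---|
| 0 | 15.0 | 1.83 | 0.86 | 0.86 |
| 10% | 13.5 | 1.74 / 1.72 | 0.79 / 0.78 | 0.83 |
| 20% | 12.0 | 1.67 / 1.64 | 0.71 / 0.69 | 0.78 |
| 30% | 10.5 | 1.61 / 1.57 | 0.62 / 0.60 | 0.72 |

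The restricted analysis keeps the 15 points and the odds ratio of 1.83. With an assumed 70% against 60%, the difference falls from 10 points to 9, 8 and 7.

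**Unequal f.** Assume no true effect (50% success in each arm) and f of 30% against 20%. Coded as successes: (0.30 + 0.70×0.5) - (0.20 + 0.80×0.5) = +5 points. Coded as failures: 0.70×0.5 - 0.80×0.5 = -5 points. The coding alone sets the direction.

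**The case against.** The strongest reply is that nothing specified in the SAP is diluted. S13 is analysed as a continuous change, which does not use the success coding. This stands. A reader might infer that low-INR patients weaken a planned comparison of success. The SAP contains no such comparison, and Protocol 9.2.2 only promises simple tests in general terms and leaves detail to the SAP. What the coding does affect is the default frequency table for categorical data in SAP 7, and any comparison built on it later.

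A reader might also infer that these patients are automatic successes, or that the result would reflect who was treated urgently rather than which product was given. Neither is supported:
- Under the *is below* reading, a patient whose INR rises to 1.5 or more still fails.
- The urgent route admits any INR, so treated urgently does not mean INR below 1.5. The number below 1.5 could be small.
- Allocation is randomised, and operating room staff are blinded until the seal is broken, just before infusion (Protocol 3.3.1.6). The decision to treat comes before allocation is known, so any imbalance in f would be by chance.

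The secondary endpoints are exploratory, and the sizes above rest on assumed rates. Both points are correct and limit the weight of the concern. They do not resolve how a patient already below 1.5 is to be coded.

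**Conclusion.** The concern holds as a gap in definition and method for one exploratory secondary endpoint. The success rule is uninformative and ambiguous for patients starting below 1.5, such patients can be treated and remain in the analysis set, and no between-group analysis of success is named. A success proportion over the whole set would mix INR response with the distribution of starting INR.

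The loss is conditional. It arises only if success is compared between arms with a common coding, and it is then a factor of about (1 - f), that is 10% to 30% of the difference for f of 10% to 30%. The range of f, the 15-point difference and the similar g in both arms are assumptions. The documents do not show that the problem is large in this trial, nor that it favours either product. The primary endpoint, its test and the sample size are untouched. This is a minor point, worth settling because it costs little.

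**What to change.** In SAP 10.3 and Appendix 1:
1. Define S13 success only for patients whose pre-IMP INR is 1.5 or more, using the same measurement from which the change is calculated.
2. Report the number with a pre-IMP INR below 1.5 by arm, outside the success denominator.
3. Add S13 success to the categorical endpoints analysed by logistic regression.
4. Keep the change in INR for all patients, with baseline INR as a covariate. This does not follow from the coding problem. It is an inexpensive gain in precision over the unadjusted ANOVA, and its size depends on a correlation that the documents do not give.

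No new data are needed: Protocol 6.1.3 already schedules INR before and after IMP initiation. Restricting on a pre-treatment value does not break the randomised comparison. The cost is SAP wording and fewer patients in the success analysis: at f = 20%, 205×0.8 = 164 per arm instead of 205. In the illustration the restricted analysis still has more power, because the difference is no longer diluted. If the team prefers to keep every patient in view, success can also be tabulated by starting INR category.
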